Table 14.3.2.8 – Duration of Most Frequently Occurring Treatment-Emergent Adverse Events (TEAEs) Related to Vascular Injection/Visual Events by MedDRA Preferred Term for As-Treated Population

Adverse Event	PN40082				Restvlane Silk			
	Events % (n/N) ¹	<7 Days % (n/N) ²	7-30 Days % (n/N) ²	>30 Days % (n/N) ²	Events % (n/N) ¹	<7 Days % (n/N) ²	7-30 Days % (n/N) ²	>30 Days % (n/N) ²
Preferred Term 1	0% (0/0)	0% (0/0)	0% (0/0)	0% (0/0)	0% (0/0)	0% (0/0)	0% (0/0)	0% (0/0)
Preferred Term 2	0% (0/0)	0% (0/0)	0% (0/0)	0% (0/0)	0% (0/0)	0% (0/0)	0% (0/0)	0% (0/0)

Most frequently occurring TEAEs related to vascular injections/visual event are those that were reported by 5% or more subjects of either treatment group.

¹ Denominator is the number of TEAEs related to vascular injections/visual event reported by all subjects who received the corresponding treatment.

² Denominator for percentages by duration is the number of subjects with respective TEAEs after receiving the corresponding treatment. Numerator (count of subjects) is based on the rule that subjects reporting more than one same incidence associated with a treatment arm are counted only once for the treatment arm under the longest duration.

Source: Listing 16.2.7.1.1

O:\Studies\Prolenium\SYM 2018-02\Biometrics\Programs\Tables\xxx.sas ran on Month Day, Year at hh:mm on data from Month Day, Year.

Table 14.3.2.9 – Overall Summary of Treatment-Emergent Adverse Events (TEAEs) Related to Vascular Injections/Visual Events for As-Treated Population

	PN40082		Restvlane Silk	
	Subjects ¹ (N=xx)	Events ² (N=xx)	Subjects ¹ (N=xx)	Events ² (N=xx)
Overall	0 (0%)	0 (0%)	0 (0%)	0 (0%)
Duration				
Less than 1 week	0 (0%)	0 (0%)	0 (0%)	0 (0%)
Between 1 week and 1 month (30 days)	0 (0%)	0 (0%)	0 (0%)	0 (0%)
More than 1 month (30 days)	0 (0%)	0 (0%)	0 (0%)	0 (0%)
Severity				
Mild	0 (0%)	0 (0%)	0 (0%)	0 (0%)
Moderate	0 (0%)	0 (0%)	0 (0%)	0 (0%)
Severe	0 (0%)	0 (0%)	0 (0%)	0 (0%)
Causality				
Treatment-related*	0 (0%)	0 (0%)	0 (0%)	0 (0%)
Not treatment-related	0 (0%)	0 (0%)	0 (0%)	0 (0%)
Outcome				
Resolved	0 (0%)	0 (0%)	0 (0%)	0 (0%)
Improved	0 (0%)	0 (0%)	0 (0%)	0 (0%)
Stabilized	0 (0%)	0 (0%)	0 (0%)	0 (0%)
Worsened	0 (0%)	0 (0%)	0 (0%)	0 (0%)
Unchanged	0 (0%)	0 (0%)	0 (0%)	0 (0%)
Treatment Required (Action Taken)				
None	0 (0%)	0 (0%)	0 (0%)	0 (0%)
Study treatment interrupted/discontinued	0 (0%)	0 (0%)	0 (0%)	0 (0%)
Non-drug therapy	0 (0%)	0 (0%)	0 (0%)	0 (0%)
New OTC or Rx drug added	0 (0%)	0 (0%)	0 (0%)	0 (0%)
Hospitalized (includes ER visits)	0 (0%)	0 (0%)	0 (0%)	0 (0%)

¹ Denominator is the number of subjects who received the corresponding treatment.

² Denominator is the number of adverse events reported by subjects who received the corresponding treatment.

*Treatment-related includes Possibly and Probably Related.

For Severity and Causality, subjects reporting more than one TEAE related to vascular injections/visual event associated with a treatment arm are counted only once for the treatment arm under the greatest reported severity and most likely causality, respectively.

Prolenium Medical Technologies Inc.
SAP Version: 1.0

Protocol: SYM 2018-02

For Duration, Outcome and Treatment Required (Action Taken), at each level of the categories, subjects reporting more than one TEAE related to vascular injections/visual event associated with a treatment arm are counted only once for the treatment arm at that category level.

Source: Listing 16.2.7.1.1

O:\Studies\Prolenium\SYM 2018-02\Biometrics\Programs\Tables\xxx.sas ran on Month Day, Year at hh mm on data from Month Day, Year.

Note:

Tables 14.3.2.1, 14.3.2.2, 14.3.2.3, 14.3.2.4 will be used as the shell for the following tables:

Table 14.3.3.1 – Treatment-Emergent Adverse Events (TEAEs) Excluding Vascular Injections/Visual Events by MedDRA System Organ Class and Preferred Term for As-Treated Population

Table 14.3.3.2 – Treatment-Emergent Adverse Events (TEAEs) Excluding Vascular Injections/Visual Events by MedDRA System Organ Class, Preferred Term, and Severity for As-Treated Population

Table 14.3.3.3 – Treatment-Emergent Adverse Events (TEAEs) Excluding Vascular Injections/Visual Events by MedDRA System Organ Class, Preferred Term, and Causality for As-Treated Population

Table 14.3.3.4 – Treatment-Emergent Adverse Events (TEAEs) Excluding Vascular Injections/Visual Events by MedDRA System Organ Class, Preferred Term, and Number of Injection for As-Treated Population

With footnote regarding data source change to “Source: Listing 16.2.7.1.2”.

Table 14.3.4.1 – Lip Function by Visit for As-Treated Population

Study Visit	Category	PN40082	Restylane Silk
Visit 1/Day 1 (Prior to injection)	N	0	0
	n (%) subjects able to sip liquid through a straw	0 (0%)	0 (0%)
Visit 2/Month 1 (Prior to touch-up)	N	0	0
	n (%) subjects able to sip liquid through a straw	0 (0%)	0 (0%)
Visit 3/Month 2	N	0	0
	n (%) subjects able to sip liquid through a straw	0 (0%)	0 (0%)
Visit 4/Month 3	N	0	0
	n (%) subjects able to sip liquid through a straw	0 (0%)	0 (0%)
Visit 5/Month 6	N	0	0
	n (%) subjects able to sip liquid through a straw	0 (0%)	0 (0%)

Source: Listing 16.2.4.8

O:\Studies\Prollenium\SYM 2018-02\Biometrics\Programs\Tables\ccx.sas ran on Month Day, Year at hh:mm on data from Month, Day, Year.

Note:

Table 14.3.4.1 will be used as the shell for the following table:

Table 14.3.4.2 – Lip Sensation Test (Cotton Wisp) by Visit for As-Treated Population

Table 14.3.4.3 – Lip Sensation Test (0.4G Monofilament) by Visit for As-Treated Population

Table 14.3.4.4 – Lip Texture Evaluation by Visit for As-Treated Population

Study Visit	Category	PN40082	Restylane Silk
Visit 1/Day 1 (Prior to injection)	N	0	0
	n (%) Normal	0 (0%)	0 (0%)
	n (%) Abnormal	0 (0%)	0 (0%)
	- n (%) Abnormal: Mild	0 (0%)	0 (0%)
	- n (%) Abnormal: Moderate	0 (0%)	0 (0%)
	- n (%) Abnormal: Severe	0 (0%)	0 (0%)
Visit 2/Month 1 (Prior to touch-up)	...		
	...		
Visit 3/Month 2			
Visit 4/Month 3			
Visit 5/Month 6			

Source: Listing 16.2.4.9

O:\Studies\Prollenium\SYM 2018-02\Biometrics\Programs\Tables\ccx.sas ran on Month Day, Year at hh:mm on data from Month, Day, Year.

Note:

Table 14.3.4.4 will be used as the shell for the following table:

Table 14.3.4.5 – Lip Firmness Evaluation by Visit for As-Treated Population

Table 14.3.4.6 – Lip Symmetry Evaluation by Visit for As-Treated Population

Table 14.3.4.7 – Lip Movement/Function Evaluation by Visit for As-Treated Population

Study Visit	Category	PN40082	Restylane Silk
Visit 1/Day 1 (Prior to injection)	N	0	0
	n (%) Normal – Subject’s ability to pucker lips	0 (0%)	0 (0%)
	n (%) Normal – Subject’s ability to blow with lips	0 (0%)	0 (0%)
	n (%) Normal – Subject’s ability to pronounce words that begin with “W”	0 (0%)	0 (0%)
Visit 2/Month 1 (Prior to touch-up)	...		
	...		
Visit 3/Month 2			
Visit 4/Month 3			
Visit 5/Month 6			

Source: Listing 16.2.4.8

O:\Studies\Prolenium\SYM 2018-02\Biometrics\Programs\Tables\ccx.sas ran on Month Day, Year at hh:mm on data from Month, Day, Year.

Table 14.3.5 – Other Analysis: Assessment of Blinding to Subjects and Evaluators at End of Study

Assessed by Subject or Evaluator	Treatment Subject Received	Treatment Guessed	n/N ¹ (%)	P-value and 90% Confidence Interval ²
By Subject	PN40082	PN40082	0/0 (0%)	(0.0%, 0.0%)
		Restylane Silk	0/0 (0%)	
		Unsure	0/0 (0%)	
	Restylane Silk	PN40082	0/0 (0%)	
		Restylane Silk	0/0 (0%)	
		Unsure	0/0 (0%)	
Overall Correct Guesses		0/0 (0%)		
By Evaluator	PN40082	PN40082	0/0 (0%)	(0.0%, 0.0%)
		Restylane Silk	0/0 (0%)	
		Unsure	0/0 (0%)	
	Restylane Silk	PN40082	0/0 (0%)	
		Restylane Silk	0/0 (0%)	
		Unsure	0/0 (0%)	
Overall Correct Guesses		0/0 (0%)		

¹ N = Total number of responses, n = number of responses associated with a given combination (e.g. number of subjects who received PN40082 and guessed Restylane Silk).

² P-values and 95% confidence intervals from the exact binomial distribution to test the null hypothesis that the proportion of correct guesses is 50%.

Source: Listing 16.2.1.2

O:\Studies\Prolenium\SYM 2018-02\Biometrics\Programs\Tables\ccx.sas ran on Month Day, Year at hh:mm on data from Month, Day, Year.

Subject Listings

Listing 16.2.1.1 – Subject Analysis Status

Site-Subject Treatment:	As-Treated (AT)		Modified Intent-to-Treat (mITT)		Per-Protocol (PP)	
	Included?	Reason for Not Included	Included?	Reason for Not Included	Included?	Reason for Not Included

O:\Studies\ Prolenium\SYM 2018-02\Biometrics\Programs\Listing\xxx.sas ran on Month Day Year at hh mm on data from Month Day, Year.

Listing 16.2.1.2 – Subject Disposition and Assessment of Blinding at End of Study

Site- Subject	Analy	Subject Disposition	Date Completed or Discontinued	Reason, if discontinued	Evaluation of Subject for Participation in PRO 2018-03 study			Subject was asked to identify treatment he received? If Yes, response	Blinded evaluating investigator was asked to identify treatment subject received? If Yes, response
					Subject underwent consent?	Subject agreed to participate?	Evaluator		
Treatment:									

Analys (Analyses): A = As-Treated (AT) Analyses, M = Modified Intent-to-Treat (MITT) Analyses, P = Per-Protocol Analyses

O:\Studies\ Prolenium\SYM 2018-02\Biometrics\Programs\Listing\xxx.sas ran on Month Day Year at hh mm on data from Month Day, Year.

Listing 16.2.1.3 – Dates of Visits

Site- Subject	Analyses	Visit 1/ Day 1 (Baseline)	Visit 2/ Month 1 Day 28 (± 2 days) [Day #]	Visit 3/ Month 2 Day 56 (± 4 days) [Day #]	Visit 4/ Month 3 Day 84 (± 4 days) [Day #]	Visit 5/ Month 6 Day 168 (± 7 days) [Day #]	No. of UVs: Unscheduled Visit(s) [Day #]
Treatment:							

Analyses: A = As-Treated (AT) Analyses, M = Modified Intent-to-Treat (MITT) Analyses, P = Per-Protocol Analyses

Day # (Study Days) = Visit Date - Baseline (Visit 1) Date +1.

O:\Studies\ Prollenium\SYM 2018-02\Biometrics\Programs\Listing\xxx.sas ran on Month Day Year at hh mm on data from Month Day, Year.

Listing 16.2.2.1 – Violation of Inclusion Criteria

Site-Subject	Analyses	1	2	3	4
--------------	----------	---	---	---	---

Treatment:

Analyses: A = As-Treated (AT) Analyses, M = Modified Intent-to-Treat (MITT) Analyses, P = Per-Protocol Analyses

*Please see section 7.3.1 of study protocol for description of the inclusion criteria.

O:\Studies\Prolenium\SYM 2018-02\Biometrics\Programs\Listing\xxx.sas ran on Month Day Year at hh mm on data from Month Day, Year.

Listing 16.2.2.2 – Violation of Exclusion Criteria

Site- Subject	Analy.	1	2	3	4	5	6	7	8	9	10	11	12	13	14	15	16	17	18	19	20	21	22	23	24	25	
Treatment:																											

Analy. (Analyses): A = As-Treated (AT) Analyses, M = Modified Intent-to-Treat (MITT) Analyses, P = Per-Protocol Analyses

*Please see section 7.3.2 of study protocol for description of the exclusion criteria.

O:\Studies\ Prolenium\SYM 2018-02\Biometrics\Programs\Listing\xxx.sas ran on Month Day Year at hh mm on data from Month Day, Year.

Listing 16.2.2.3 – Significant Protocol Violations

Site-Subject	Analyses	Significant Protocol Violation
--------------	----------	--------------------------------

Treatment:

Analyses: A = As-Treated (AT) Analyses, M = Modified Intent-to-Treat (MITT) Analyses, P = Per-Protocol Analyses

Significant protocol violations are those events that exclude subjects from any analysis population.

O:\Studies\ Prolenium\SYM 2018-02\Biometrics\Programs\Listing\xxx.sas ran on Month Day Year at hh mm on data from Month Day, Year.

Listing 16.2.2.4 – Comments

Site-Subject	Analyses	Date of Comments	CRF Page Number	Comment(s)	Initials
--------------	----------	------------------	--------------------	------------	----------

Treatment:

Analyses: A = As-Treated (AT) Analyses, M = Modified Intent-to-Treat (MITT) Analyses, P = Per-Protocol Analyses

O:\Studies\ Prolenium\SYM 2018-02\Biometrics\Programs\Listing\xxx.sas ran on Month Day Year at hh mm on data from Month Day, Year.

Listing 16.2.4.1 – Demographics

Site- Subject	Subject Initials	Analyses	Age (yrs)	Sex	Race	Ethnicity	Fitzpatrick Skin Type	Informed Consent	
								Signed?	Date

Treatment:

Analyses: A = As-Treated (AT) Analyses, M = Modified Intent-to-Treat (MITT) Analyses, P = Per-Protocol Analyses

O:\Studies\ Prolenium\SYM 2018-02\Biometrics\Programs\Listing\xxx.sas ran on Month Day Year at hh:mm on data from Month Day, Year.

Listing 16.2.4.2 – Brief Physical Examination at Baseline

Site-Subject	Analyses	Height (inches)	Weight (lbs)	Physical Examination		
				Heart	Lungs	Abdomen
Treatment:						

Analyses: A = As-Treated (AT) Analyses, M = Modified Intent-to-Treat (MITT) Analyses, P = Per-Protocol Analyses

O:\Studies\Prolenium\SYM 2018-02\Biometrics\Programs\Listing\xxx.sas ran on Month Day Year at hh mm on data from Month Day, Year.

Listing 16.2.4.3 – Medical History Findings

Site-Subject	Analyses	Medical System	Diagnosis/Procedure	Onset Date	Stop Date	Concomitant Medication?
Treatment:						
		XXXXXXX	XXXXXXXXXXXX	----1997	Ongoing	No

Analyses: A = As-Treated (AT) Analyses, M = Modified Intent-to-Treat (MITT) Analyses, P = Per-Protocol Analyses

O:\Studies\Prolenium\SYM 2018-02\Biometrics\Programs\Listing\xxx.sas ran on Month Day Year at hh mm on data from Month Day, Year.

Listing 16.2.4.4 – Prior and Concomitant Medications/Treatments

Site- Subject	Analy	If Used on Face	WHO Class // WHO Name // Medication	Indication	Start Date [Day #]	Stop Date [Day #]	Dosage	Freq.	Route
Treatment:		QD1	XXXXXXXXXX // XXX // XXXXXXXXXXXX XXXXXXXXXX	XXXXXXXXXX	01JAN05 [3]	Ongoing	xxxxx	xxxx	xxx

Analy (Analyses): A = As-Treated (AT) Analyses only, M = Modified Intent-to-Treat (MITT) Analyses, P = Per-Protocol Analyses

Note: Medications coded using the WHO Drug Dictionary, version xxx.

Day # is calculated from baseline (Visit 1) date. Day 1 is the baseline date while Day -1 is the day prior to the baseline visit. L=Left side of the face, R=Right side of the face.

O:\Studies\ Prolenium\SYM 2018-02\Biometrics\Programs\Listing\xxx.sas ran on Month Day Year at hh:mm on data from Month Day, Year.

Listing 16.2.4.5 – Non-Pharmacological Interventions (NPIs)

Site- Subject	Analy	If Used on Face	Non-Pharmacological Intervention	Indication	Start Date [Day #]	Stop Date [Day #]	Dosage	Freq.	Route
Treatment:									
		QD1,QD2	XXXXXXXXXX XXX XXXXXXXXXXX	XXXXXXXX	01JAN05 [3]	Ongoing	xxxxx	xxxx	xxx

Analy (Analyses): A = As-Treated (AT) Analyses only, M = Modified Intent-to-Treat (MITT) Analyses, P = Per-Protocol Analyses

Day # is calculated from baseline (Visit 1) date. Day 1 is the baseline date while Day -1 is the day prior to the baseline visit. L=Left side of the face, R=Right side of the face.

O:\Studies\ Prolenium\SYM 2018-02\Biometrics\Programs\Listing\xxx.sas ran on Month Day Year at hh:mm on data from Month Day, Year.

Listing 16.2.4.6 – Vital Signs and Urine Pregnancy Test at Baseline

Site-Subject	Analyses	Sitting Systolic BP (mmHg)	Sitting Diastolic BP (mmHg)	Heart Rate (bpm)	Oral Temperature (°F)	Respiratory Rate (breath/min)	Urine Pregnancy Test	
							Test Results	Test Date
Treatment:								

Analyses: A = As-Treated (AT) Analyses only, M = Modified Intent-to-Treat (MITT) Analyses, P = Per-Protocol Analyses

O:\Studies\ Prolenium\SYM 2018-02\Biometrics\Programs\Listing\xxx.sas ran on Month Day Year at hh:mm on data from Month Day, Year.

Listing 16.2.4.7 – Vision Evaluation

Site- Subject	Analyses	Study Visit (Time Point)	Confrontational Visual Field Results (Specify if abnormal)	Ocular Visual Field Results (Specify if abnormal)	Subject wearing corrective lenses?	Snellen Visual Acuity Score		Vision at Post-Baseline Visit	
						Left Eye	Right Eye	Initials of Assessor	Changed significantly from baseline?
Treatment:									

Analyses: A = As-Treated (AT) Analyses, M = Modified Intent-to-Treat (MITT) Analyses, P = Per-Protocol Analyses

O:\Studies\ Prolenium\SYM 2018-02\Biometrics\Programs\Listing\xxx.sas ran on Month Day Year at hh mm on data from Month Day, Year.

Listing 16.2.4.8 – Lip Function, Lip Sensation and Lip Movement/Function Tests

Site- Subject	Analyses	Study Visit (Time Point)	Able to sip liquid through a straw?	Assessor of Lip Function	Able to feel sensation of a cotton wisp?	Able to feel sensation of a 0.4G monofilament	Assessor of Lip Sensation	Ability to pucker lips	Ability to blow with lips	Ability to pronounce words that begin with “W”	Assessor of Lip Movement /Function
------------------	----------	-----------------------------	--	--------------------------------	---	--	---------------------------------	------------------------------	---------------------------------	---	---

Treatment:

Analyses: A = As-Treated (AT) Analyses, M = Modified Intent-to-Treat (MITT) Analyses, P = Per-Protocol Analyses

O:\Studies\Prolenium\SYM 2018-02\Biometrics\Programs\Listing\xxx.sas ran on Month Day Year at hh mm on data from Month Day, Year.

Listing 16.2.4.9 – Lip Texture, Lip Firmness and Lip Symmetry Evaluations

Site-Subject	Analyses	Study Visit (Time Point)	Lip Texture		Lip Firmness		Lip Symmetry	
			Normal or Abnormal (severity)	Evaluator	Normal or Abnormal (severity)	Evaluator	Normal or Abnormal (severity)	Evaluator
Treatment:								

Analyses: A = As-Treated (AT) Analyses, M = Modified Intent-to-Treat (MITT) Analyses, P = Per-Protocol Analyses

O:\Studies\Prolenium\SYM 2018-02\Biometrics\Programs\Listing\xxx.sas ran on Month Day Year at hh mm on data from Month Day, Year.

Listing 16.2.5.1 – Treatment Administration at Visit 1/Day 1 and Visit 2/Month 1

Site- Subject	Analy	Random Number	Visit Number	Injection placed successfully?	Site of Injection	Time of Injection	Amount of Syringe Used (ml)	Injection Techniques Used	Depth of Injection	Initials Who Performed Injection	Investigator Ease of Use Assessment	Evaluator
------------------	-------	------------------	-----------------	--------------------------------------	----------------------	----------------------	-----------------------------------	---------------------------------	--------------------	--	---	-----------

Treatment:

Analy (Analyses): A = As-Treated (AT) Analyses, M = Modified Intent-to-Treat (MITT) Analyses, P = Per-Protocol Analyses

Investigator Ease of Use Assessment assess on the Numerical Rating Scale (NRS): 0 (Not Easy) to 10 (Most Easy).

O:\Studies\ Prollenium\SYM 2018-02\Biometrics\Programs\Listing\xxx.sas ran on Month Day Year at hh mm on data from Month Day, Year.

Listing 16.2.6.1.1 – Efficacy Evaluations of Lip Fullness Grading Scale (LFGS)

Site-Subject	Analyses	Study Visit	By Treating Investigator or Blinded Evaluating Investigator	Overall Rating	Upper Lip Rating	Lower Lip Rating	Initials of Who Performed Assessment
--------------	----------	-------------	---	----------------	------------------	------------------	--

Treatment:

Analyses: A = As-Treated (AT) Analyses, M = Modified Intent-to-Treat (MITT) Analyses, P = Per-Protocol Analyses

O:\Studies\Prolenium\SYM 2018-02\Biometrics\Programs\Listing\xxx.sas ran on Month Day Year at hh mm on data from Month Day, Year.

Listing 16.2.6.1.2 – Efficacy Evaluations of Perioral Lines at Rest Severity Scale (POL)

Site-Subject	Analyses	Study Visit	By Treating Investigator or Blinded Evaluating Investigator	Overall Rating	Upper Lip Rating	Lower Lip Rating	Assessment Performed By
--------------	----------	-------------	---	----------------	------------------	------------------	----------------------------

Treatment:

Analyses: A = As-Treated (AT) Analyses, M = Modified Intent-to-Treat (MITT) Analyses, P = Per-Protocol Analyses

O:\Studies\Prolenium\SYM 2018-02\Biometrics\Programs\Listing\xxx.sas ran on Month Day Year at hh mm on data from Month Day, Year.

Listing 16.2.6.1.3 – Efficacy Evaluations of Subject Satisfaction with Lips, Swelling and Global Aesthetic Improvement

Site- Subject	Analyses	Study Visit	Subject	Swelling Assessment		Patient Global Aesthetic	Investigator Global Aesthetic Improvement	
			Satisfaction with Lips VAS	Grade	Performed By	Improvement (pGAI)	Score	(iGAI) Performed By
Treatment:								

Analyses: A = As-Treated (AT) Analyses, M = Modified Intent-to-Treat (MITT) Analyses, P = Per-Protocol Analyses

O:\Studies\ Prolenium\SYM 2018-02\Biometrics\Programs\Listing\xxx.sas ran on Month Day Year at hh mm on data from Month Day, Year.

Listing 16.2.6.2.1 – Derived Overall Lip Fullness Grading Scale (LFGS) for Modified Intent-to-Treat Population

Site-Subject	Fitzpatrick skin type	Lips Treated	Visit 1	Visit 2	Visit 3	Visit 4	Visit 5
Treatment: XX-XXX	II	Both	1	2	3	2	2, 3, 2, 2, 3

LFGS: 0=Very Thin Lips, 1=Thin Lips, 2=Moderately Thick Lips, 3=Thick Lips, 4=Full Lips.

Note: The 5 entries contained under a visit for a subject are the 5 imputed LFGS scores for the missing value through multiple imputations.

O:\Studies\ Prollenium\SYM 2018-02\Biometrics\Programs\Listing\xxx.sas ran on Month Day Year at hh mm on data from Month Day, Year.

Listing 16.2.6.2.2 – Derived Primary and Secondary Efficacy Responses on Overall LFGS and Overall POL for Modified Intent-to-Treat Population

Site-Subject	Study Visit	Lip Fullness Grading Scale (LFGS)			Perioral Lines at Rest Severity Scale (POL)		
		Overall LFGS Rating	Change from Baseline	Treatment Success [†]	Overall POL Rating	Change from Baseline	Responder ^{**}
Treatment:							
XX-XXX	4	2	-1	Y			
	5	2, 3, 2, 2, 3	-1, -2, -1, -1, -2	Y, Y, Y, Y, Y			

Change from Baseline for Visit x = Baseline – Visit x, where x=2, 3, 4, 5.

[†]Treatment success is defined as an achievement of at least a 1-grade increase from baseline on the overall LFGS.

^{**}Responder is defined as a subject demonstrating at least 1-point improvement, i.e., decrease in severity, from baseline POL severity.

Note: The 5 entries contained under a visit for a subject are associated the 5 imputed LFGS scores for the missing value through multiple imputations.

O:\Studies\ Prolenium\SYM 2018-02\Biometrics\Programs\Listing\cxc.sas ran on Month Day Year at hh mm on data from Month Day, Year.

Listing 16.2.6.2.3 – Derived Primary and Secondary Efficacy Responses on Overall LFGS and Overall POL for Per-Protocol Population

Site-Subject	Study Visit	Lip Fullness Grading Scale (LFGS)			Perioral Lines at Rest Severity Scale (POL)		
		Overall LFGS Rating	Change from Baseline	Treatment Success*	Overall POL Rating	Change from Baseline	Responder**
Treatment:							

Change from Baseline for Visit x = Baseline – Visit x, where x=2, 3, 4, 5.

*Treatment success is defined as an achievement of at least a 1-grade increase from baseline on the overall LFGS.

**Responder is defined as a subject demonstrating at least 1-point improvement, i.e., decrease in severity, from baseline POL severity.

O:\Studies\Prolenium\SYM 2018-02\Biometrics\Programs\Listing\xxx.sas ran on Month Day Year at hh mm on data from Month Day, Year.

Listing 16.2.6.2.4 – Derived Other Efficacy Responses Based on Observed Data: LFGS and POL for Upper/Lower Lip

Site- Subject	Analyses	Study Visit	Upper or Lower Lip	Lip Fullness Grading Scale (LFGS)			Perioral Lines at Rest Severity Scale (POL)		
				LFGS Rating	Change from Baseline	Treatment Success*	POL Rating	Change from Baseline	Responder**
Treatment:									

Change from Baseline for Visit x = Baseline – Visit x, where x=2, 3, 4, 5.

*Treatment success is defined as an achievement of at least a 1-grade increase from baseline on the overall LFGS.

**Responder is defined as a subject demonstrating at least 1-point improvement, i.e., decrease in severity, from baseline POL severity.

O:\Studies\Prolenium\SYM 2018-02\Biometrics\Programs\Listing\xxx.sas ran on Month Day Year at hh mm on data from Month Day, Year.

Listing 16.2.7.1.1 – Adverse Events (Related to Vascular Injections/Visual Events)

Site- Subject	Analy	FST	Reported by	System Organ Class// Preferred Term// Verbatim Term	Start Date Time [Day #]	Stop Date Time [Day #]	Severity Causality Outcome	Where on face Rel. to injection? Vision related?	Action Taken ¹	SAE
Treatment:										
xx-xxx	A	III	Subj/Diary	GENERAL DISORDERS AND ADMINISTRATION	01JAN2019	04JAN2019	MILD	QD1, QD3	3,4	N
				SITE CONDITIONS//						
				INJECTION SITE SWELLING//	13:25	08:30	PROBABLY	Y		
				SWELLING ON FACE	2	5	STABLIZED	N		

Analy (Analyses): A = As-Treated (AT) Analyses only, M = Modified Intent-to-Treat (MITT) Analyses, P = Per-Protocol Analyses

Day # is calculated from baseline (Visit 1) date. Day 1 is the baseline date while Day -1 is the day prior to the baseline visit.

¹ Action Taken: 1=None, 2=Study treatment interrupted/discontinued, 3=Non-drug therapy, 4=New OTC or Rx drug added, 4=Hospitalized

O:\Studies\ Prolenium\SYM 2018-02\Biometrics\Programs\Listing\xxx.sas ran on Month Day Year at hh mm on data from Month Day, Year.

Listing 16.2.7.1.2 – Adverse Events (Excluding Vascular Injections/Visual Events)

Site-Subject	Analy	FST	Reported by	System Organ Class// Preferred Term// Verbatim Term	Start Date [Day #]	Stop Date [Day #]	Severity Causality Outcome	Where on face	Action Taken ¹	SAE
xx-xxx	M	III	Subj/Diary	NERVOUS SYSTEM DISORDERS// HEADACHE // HEADACHE	01JAN2019 2	04JAN2019 5	MILD UNLIKELY STABLIZED	QD1,QD3	1	N

Analy (Analyses): A = As-Treated (AT) Analyses only, M = Modified Intent-to-Treat (MITT) Analyses, P = Per-Protocol Analyses

Day # is calculated from baseline (Visit 1) date. Day 1 is the baseline date while Day -1 is the day prior to the baseline visit.

¹ Action Taken: 1=None, 2=Study treatment interrupted/discontinued, 3=Non-drug therapy, 4=New OTC or Rx drug added, 4=Hospitalized
O:\Studies\Prollenium\SYM 2018-02\Biometrics\Programs\Listing\xxx.sas ran on Month Day Year at hh mm on data from Month Day, Year.

Note:

Repeat Listings 16.2.7.1.1 and 16.2.7.1.2 for AEs that led to study treatment interrupted/Discontinued and Serious AEs –

Listing 16.2.7.2.1 – Adverse Events (Related to Vascular Injections/Visual Events) Leading to Study Treatment Interrupted/Discontinued

Listing 16.2.7.2.2 – Adverse Events (Excluding Vascular Injections/Visual Events) Leading to Study Treatment Interrupted/Discontinued

Listing 16.2.7.3.1 – Serious Adverse Events (Related to Vascular Injections/Visual Events)

Listing 16.2.7.3.2 – Serious Adverse Events (Excluding Vascular Injections/Visual Events)

Listing 16.2.7.4 – Adverse Events (Related to Vascular Injections/Visual Events) Lasted more than 30 Days

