In the overall population of subjects receiving their initial treatment with *Restylane Silk*, 12 severe events occurred in 6 subjects. Ten of the severe events were Lip Swelling which occurred in 5 subjects. There were 80 moderate events which occurred in 34 subjects (16%). There were 5 serious adverse events in three patients during the study. In the No Treatment group there were incidences of Clostridial Infection (n=1), and Urinary Tract Obstruction (n=1). In the *Restylane Silk* group there were Cystitis (n=1), Intervertebral Disc Protrusion (n=1), and Nephrolithiasis (n=1). None of the serious events were reported as related to treatment with *Restylane Silk*.

Nineteen subjects reported AEs associated with treatment of the lip whose onset was more than 3 weeks after a *Restylane Silk* injection. There were a total of 35 events in the lip reported in these 19 subjects. Most of the events were Lip Swelling (26/35; 74%) and also included Lip Disorder (6/35; 17%), Lip Pain/Pain 2/35; 6%), and Contusion (1/35; 3%). None of the events were reported as serious and all of the events were reported as either mild (24/35; 69%) or moderate (11/35; 31%).

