5.6.1 Adverse Events

All adverse events (AEs) occurring during the study will be recorded and coded in the Medical Dictionary for Regulatory Activities (MedDRA), version 20 or higher. TEAEs are defined as events that appear subsequent to the first injection or that were present prior to the first injection but worsened in intensity after the first injection.

Frequency and percent of subjects reporting TEAEs will be tabulated for each treatment by system organ class and preferred terms, and further by severity and relationship to study device. In summaries of severity and relationship, subjects who reported more than one event in a treatment arm that are mapped to the same preferred term will be counted only once in that treatment arm under the strongest severity and relationship, respectively.

TEAEs related to vascular injections/Visual events will also be tabulated by subject Fitzpatrick Skin Type (I-III vs. IV-VI), each Fitzpatrick Skin Type individually and by number of injections subjects received. Most frequently occurring TEAEs related to vascular injections/Visual events (those reported by 5% or more subjects of either treatment group) will be tabulated by preferred term. These TEAEs will also be summarized by event's severity and duration.

Treatment-Emergent Serious Adverse Events (TESAEs) and TEAEs that led to treatment interruption or discontinuation will be presented in data listings.

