System Organ Class Preferred Term	PN40082		Restvlane Silk	
	1 Injection (N=xx)	2 Injections (N=xx)	1 Injection (N=xx)	2 Injections (N=xx)
Class 1	0 (0%)	0 (0%)	0 (0%)	0 (0%)
Term 1	0 (0%)	0 (0%)	0 (0%)	0 (0%)
Term 2	0 (0%)	0 (0%)	0 (0%)	0 (0%)
Class 2	0 (0%)	0 (0%)	0 (0%)	0 (0%)
Term 1	0 (0%)	0 (0%)	0 (0%)	0 (0%)

...

TEAEs are grouped by number of injection(s) a subject received up to when the events started. 1 Injection = ON or AFTER the injection on Day 1 AND BEFORE the touch up. 2 Injections = ON or AFTER the touch up.

Note: The denominator for a grouping includes all the subjects who went through the indicated period regardless if they reported any TEAEs during the period.

Counts reflect numbers of subjects reporting one or more TEAE related to vascular injections/visual event that map to the MedDRA (version x x) system organ class/preferred term. At each level of summarization (system organ class or preferred term), subjects reporting more than one event are counted only once.

Source: Listing 16.2.7.1.1

O:\Studies\Prolenium\SYM 2018-02\Biometrics\Programs\Tables\xxx.sas ran on Month Day, Year at hh:mm on data from Month Day, Year.

Table 14.3.2.5 – Treatment-Emergent Adverse Events (TEAEs) Related to Vascular Injections/Visual Events by MedDRA System Organ Class, Preferred Term, and Fitzpatrick Skin Type (FST) for As-Treated Population

System Organ Class Preferred Term	Treatment Group	FST I (N=xx)	FST II (N=xx)	FST III (N=xx)	Pooled FST I-III (N=xx)	FST IV (N=xx)	FST V (N=xx)	FST VI (N=xx)	Pooled FST IV-VI (N=xx)
Subjects with at Least One Injection- Site or Visual TEAE	PN40082	0 (0%)	0 (0%)	0 (0%)	0 (0%)	0 (0%)	0 (0%)	0 (0%)	0 (0%)
	Restvlane Silk	0 (0%)	0 (0%)	0 (0%)	0 (0%)	0 (0%)	0 (0%)	0 (0%)	0 (0%)
Class 1	PN40082	0 (0%)	0 (0%)	0 (0%)	0 (0%)	0 (0%)	0 (0%)	0 (0%)	0 (0%)
	Restvlane Silk	0 (0%)	0 (0%)	0 (0%)	0 (0%)	0 (0%)	0 (0%)	0 (0%)	0 (0%)
Term 1	PN40082	0 (0%)	0 (0%)	0 (0%)	0 (0%)	0 (0%)	0 (0%)	0 (0%)	0 (0%)
	Restvlane Silk	0 (0%)	0 (0%)	0 (0%)	0 (0%)	0 (0%)	0 (0%)	0 (0%)	0 (0%)
...									
...									
...									

Counts reflect numbers of subjects reporting one or more TEAE related to vascular injections/visual event that map to the MedDRA (version x x) system organ class/preferred term. At each level of summarization (system organ class or preferred term), subjects reporting more than one event are counted only once.

Source: Listing 16.2.7.1.1

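### The AE tables by number of injections show crude percentages over unequal time at risk, so for later-onset events the injection count is confounded with follow-up time (minor)

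*SAP*

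**What the plan says.** SAP 5.6.1 commits to tabulating one family of treatment-emergent events by "each Fitzpatrick Skin Type individually and by number of injections subjects received". The shell is Table 14.3.2.4. Its footnotes set four rules:

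- Allocation: "TEAEs are grouped by number of injection(s) a subject received up to when the events started".
- Periods: "1 Injection = ON or AFTER the injection on Day 1 AND BEFORE the touch up", and "2 Injections = ON or AFTER the touch up".
- Denominator: "The denominator for a grouping includes all the subjects who went through the indicated period regardless if they reported any TEAEs during the period".
- Numerator: at each level of summarisation, "subjects reporting more than one event are counted only once".

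Cells are n (%). The note after Table 14.3.2.9 reuses the shell for Table 14.3.3.4, which covers the remaining events. SAP 5.6.2, on exposure, summarises only the amount of product used. Neither the text nor the shells give person-time, an exposure-adjusted rate or a common window for these tables.

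**The concern.** The footnote closes the one-injection period only at a touch-up. By the allocation rule, a subject who never has one keeps every event through to the end of the study in that column. A touched-up subject leaves it at about Day 28 and spends the rest of the study in the other column. Each counts as one in the denominator, whatever the time observed.

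A table laid out by number of injections invites two readings: whether events become more frequent after a second session, and whether the devices differ after one or two. For events that start weeks or months after injection, the first reading mixes injection count with length of observation. The second does so as well if the arms differ in how often a touch-up is given.

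**Working it through.** The plan states no person-time, touch-up rate or event rate for these tables, so there is no figure of its own to reproduce.

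**Period lengths.** Visit days are in SAP 3.1. Listing 16.2.1.3 makes baseline Day 1, so elapsed days = day number − 1.

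- One injection, touched up at Visit 2 (Day 28 ± 2): 28 − 1 = 27 days (25 to 29).
- One injection, never touched up, to Visit 5 (Day 168 ± 7): 168 − 1 = 167 days (160 to 174).
- Two injections: 168 − 28 = 140 days.

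Mean time in the one-injection column at touch-up rate t is 27t + 167(1 − t): 125 days at 30%, 97 at 50%, 83 at 60% and 69 at 70%.

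**Within an arm.** Assume a constant hazard, no effect of the touch-up, and a 167-day risk R. Then R(d) = 1 − (1 − R)^(d/167), and the one-injection column shows t·R(27) + (1 − t)·R.

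At R = 30%, R(27) = 5.6% and R(140) = 25.8%. With t = 50%, the one-injection column shows 0.5 × 5.6 + 0.5 × 30 = 17.8%, against 25.8% for two injections. Over a range of assumptions:

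| Six-month risk R | Touch-up rate | One injection | Two injections |
|---|---|---|---|
| 10% | 50% | 5.8% | 8.5% |
| 30% | 30% | 22.7% | 25.8% |
| 30% | 50% | 17.8% | 25.8% |
| 30% | 70% | 12.9% | 25.8% |
| 50% | 50% | 30.3% | 44.1% |

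**Between arms, late-onset lip events.** The comparator's Instructions for Use, attached to the protocol, report that "Nineteen subjects reported AEs associated with treatment of the lip whose onset was more than 3 weeks after a" Restylane Silk injection; the Warnings section gives delayed onset at 21 to 142 days. Assume 218 treated subjects as the denominator: 19/218 = 8.7%. Spread onsets evenly over 21 to 142 days, so that (142 − 27)/(142 − 21) = 95% fall after day 27: 8.7% × 0.95 = 8.3%.

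- Touch-up 30% v 60%: 8.3 × (0.70 − 0.40) = 2.5 points.
- Touch-up 40% v 50%: 8.3 × 0.10 = 0.8 points, or 0.9 if all 8.7% start after the touch-up.
- Equal rates: 0.

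**Between arms, events spread evenly over follow-up.** With the same hazard in both arms, 30% v 60% gives 2.5, 7.3 and 11.8 points at R = 10%, 30% and 50%; 40% v 50% gives 0.8, 2.4 and 3.9 points.

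**With an equal window.** Under the same constant hazard at R = 30%, a 25-day window gives 1 − 0.70^(25/167) = 5.2% in every column, whatever the touch-up rates.

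**The case against.** The table is descriptive: it has no test, interval or difference column, and SAP 5.6.1 promises only a tabulation. No endpoint or claim depends on it. Allocating an event by injections received at onset is a legitimate grouping. Column Ns show the touch-up counts, the listings give every onset day, and SAP Section 6 allows the shells to be modified. All of this stands, and it keeps the point minor.

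Three stronger readings are tempting.

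- **That the comparison of safety between devices is distorted.** The documents do not support this. Tables 14.3.2.1 to 14.3.2.3 and 14.3.3.1 to 14.3.3.3 cover the whole study by arm and are not split at touch-up. Within the split tables, a difference between arms needs unequal touch-up rates. If the devices call for touch-ups equally often and are handled alike, randomisation makes the expected rates equal. Unequal rates are possible, because touch-up is at the discretion of the unblinded Treating Investigator (Protocol 7.6.1, 7.7.3) and the gels differ in concentration (25 v 20 mg/mL, Protocol 7.4.1). No rate is stated.
- **That a gap of about 2.5 points should be expected.** It is an upper-end illustration. The 30% v 60% split is assumed. The label gives no denominator for the 19 subjects, and 133 of the 218 also had a second treatment, so 8.7% is not shown to be a one-session risk. Counting once per term shrinks it further: 26 of the 35 late events were lip swelling, which 43% reported after first treatment. Taking the event share as a subject share and assuming independence, the lip-swelling row moves about 2.5 × 0.74 × 0.57 = 1.1 points. For scale, 5.8% v 3.3% (0.70 and 0.40 of 8.3%) at 79 per arm has a standard error of √(5.8 × 94.2/79 + 3.3 × 96.7/79) = 3.3 points.
- **That equal windows would show the effect of a second injection.** They would not. Touched-up subjects are a selected group, and equalising time does not remove that.

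The within-arm problem survives these objections. It needs no difference between arms, and visible column Ns do not show how long each subject was observed.

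**Conclusion.** The point holds as a minor presentation flaw. The period lengths of about 27, 167 and 140 days follow directly from the schedule and the footnote, and nothing elsewhere in the SAP corrects for them. For events starting after about Day 28, time at risk is confounded with number of injections within each arm. The 17.8% v 25.8% example rests on an assumed 50% touch-up rate, 30% risk and constant hazard. Any between-arm effect is conditional on unequal touch-up rates and on onsets after about Day 28; the touch-up rates and risks used to size it are assumptions. Reactions in the first days after a session are essentially unaffected, because both columns observe that period in full.

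**What to change.** In Tables 14.3.2.4 and 14.3.3.4:

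1. Count events with onset in an equal window after each session: Days 0-24 after the first injection, censored before any touch-up, and Days 0-24 after the touch-up. The earliest in-window touch-up is Day 26, which is 25 days after Day 1, so a first window running to Day 25 would include the touch-up day. Censoring is still needed because Protocol 7.5 tolerates visits outside the window.
2. Use all treated subjects as the first denominator and touched-up subjects as the second.
3. Show later-onset events separately, per 100 subject-months, by number of injections received, so that delayed reactions stay visible.
4. Add a footnote that touch-up is discretionary and that the contrast between one and two injections is descriptive, not causal.

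This needs an SAP footnote, a small amount of extra programming and some table space. No new data are required.
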